12.1. Extent of Exposure

Extent of exposure to dabrafenib and trametinib will be summarized separately.

The duration of exposure to study treatment in weeks (from first day to last day of treatment) will be summarised. Descriptive statistics including mean, median, standard deviation, minimum, and maximum will be calculated for time on study treatment. Moreover, time on study treatment will be categorized in different time period: < 2 months, 2 months to 4 months, >4 months to 8 months and >8 months.

The subject daily dose, defined as the cumulative dose divided by the duration of exposure for each subject, will be summarized. In addition, summary of the population level daily dose will also be provided. In this analysis, a dose on each day for each subject will be treated as an observation and the summary will be based on the dose on each individual day for all subjects.

Example of population level daily dose:

- Take 2 Subjects
 - Subject 1 dose dates:
 - 150 mg BID 01JAN2014-10JAN2014
 - 150 mg BID 13JAN2014-22JAN2014
 - Subject 2 dose dates:
 - 150 mg BID 01JAN2014-10JAN2014
 - 100 mg BID 11JAN2014-20JAN2014
 - Population level daily dose (See equation below):

$$\text{Population Level Daily Dose} = \frac{[(10 * 300) + (10 * 300) + (10 * 300) + (10 * 200)]}{(10 + 2 + 10 + 10 + 10)}$$

$$= 262\text{¶}$$

Dose reductions will be summarised by number of reductions and reasons for reductions. Dose escalations will be summarised by number of escalations and reasons for escalation. Dose interruptions will be summarised by number of interruptions, reasons for the interruptions, and interruption duration (days). The mean, standard deviation, median, minimum value, and maximum value will be computed for the duration of interruptions as well as the number and percentage of the interruptions ≤ 7 , 8 -14, 15 - 21 and >21 days. The summaries of dose modifications will be provided only if the data warrant.

All the dose reductions, dose escalations and dose interruptions will be listed separately.

The cumulative exposure plot will be provided showing the proportion of subjects on treatment over time.

12.2. Adverse Events

An overview summary of AEs, including counts and percentages of subjects with any AE, AEs related to study treatment, AEs leading to permanent discontinuation of study treatment, AE leading to dose reductions, AEs leading to dose interruptions, SAEs, SAEs related to study treatment, fatal SAEs, and fatal SAEs related to study treatment will be produced.

A summary of non-serious AEs that occurred in strictly 5% of the subjects or above will be provided (no rounding for the percentage will be used in terms of 5% threshold, e.g. event with 4.9% incidence rate should not be included in this table). The summary will be displayed by System Organ Class (SOC) and Preferred Term (PT). Another summary will be created that highlights the number of subjects with Non-Serious AE, total number of exposed subjects, and number of non-serious AEs for any European submissions.

The relationship between Medical Dictionary for Regulatory Affairs (MedDRA) SOC, PT, and Verbatim Text will be displayed.

Adverse events (AEs) will be graded according to the CTCAE, Version 4.0. Adverse events will be coded to the preferred term (PT) level using the MedDRA dictionary.

A summary of number and percentage of subjects with any adverse events by maximum grade will be produced. AEs will be sorted by Preferred term (PT) in descending order of total incidence first and then by each treatment arm. The summary will use the following algorithms for counting the subject:

- **Preferred term row:** Subjects experiencing the same AE preferred term several times with different grades will only be counted once with the maximum grade.
- **Any event row:** Each subject with at least one adverse event will be counted only once at the maximum grade no matter how many events they have.

In addition, the frequency and percentage of AEs (all grades) will be summarized and displayed in two ways: 1) in descending order of total incidence first and then by each treatment arm by PT only and 2) in descending order of total incidence first and then by each treatment arm by System Organ Classes (SOC) and PT. In the SOC row, the number of subjects with multiple events under the same system organ class will be counted once.

A separate summary will be provided for study treatment-related AEs. A study treatment-related AE is defined as an AE for which the investigator classifies the relationship to study treatment as “Yes”. A worst case scenario approach will be taken to handle missing relatedness data, i.e. the summary table will include events with the relationship to study treatment as ‘Yes’ or missing. The summary table will be displayed in descending order of total incidence first and then by each treatment arm by PT only.

12.3. Adverse Events of Special Interest

A comprehensive list of MedDRA terms based on clinical review will be used to identify each adverse event of special interest. Change to the MedDRA dictionary may occur between the start of the study and the time of reporting and/or emerging data from on-going studies may highlight additional adverse events of special interest, therefore the list of MedDRA terms to be used for each event of interest and the specific adverse events of interest will be based on the safety review team agreement at the time of reporting. The list of MedDRA terms for each adverse event of special interest will be provided.

For subjects receiving dabrafenib monotherapy, the adverse events of special interest include but not be limited to the following:

- Cutaneous squamous cell carcinoma (cuSCC) including keratoacanthoma (KA),
- Pyrexia events
- Treatment-emergent malignancies (excluding cuSCC/KA, and cancer under study)
- Renal failure/acute renal failure events
- Uveitis
- Hypersensitivity events
- Pancreatitis events
- Hyperglycemia events

For subjects receiving trametinib monotherapy, the adverse events of special interest include but not be limited to the following:

- Skin-related toxicities (including rash)
- Diarrhoea
- Left Ventricular dysfunction (including ejection fraction decreasing)
- Ocular Events
- Pneumonitis
- Hepatic disorders
- Hypertension
- Oedema
- Hypersensitivity
- Bleeding events

For subjects receiving dabrafenib and trametinib in either the combination arm of after 8 weeks of monotherapy, the adverse events of special interest include but not be limited to the following:

- Cutaneous squamous cell carcinoma (cuSCC) including keratoacanthoma (KA),
- Pyrexia events
- Treatment-emergent malignancies (excluding cuSCC/KA, and cancer under study)
- Renal failure/acute renal failure events
- Uveitis
- Hypersensitivity events
- Pancreatitis events
- Hyperglycaemia events
- Skin-related events (exclude SCC, KA)
- Diarrhoea
- Cardiac-related events
- Ocular events
- Pneumonitis events
- Hepatic events
- Oedema events
- Hemorrhages events
- Hypertension
- Neutropenia events
- Pulmonary embolism events

All AEs of special interest will be summarized by categories of AE of special interest, preferred term and maximum toxicity grade in one table per treatment regimen (dabrafenib monotherapy, trametinib monotherapy, and dabrafenib plus trametinib combotherapy). AEs of special interest will be sorted by categories and then by preferred term in descending order based on incidence.

The following displays will be provided for selected AEs of special interest occur in > 5 subjects per treatment regimen:

- Summary of characteristics of AE of special interest, which will summarize event characteristics (serious, study treatment-related, fatal), number of occurrences, number of subjects, maximum toxicity, outcome, and action taken. The worst case approach will be applied at subject level for the event outcome and maximum grade, i.e. a subject will only be counted once as the worst case from all the events experienced by the subject. For action taken to a event, subject will be counted once under each action, e.g. if a subject has a event leading to both study treatment discontinuation and dose reduction, the

subject will be counted once for study treatment discontinuation and dose reduction, respectively.

- Summary of onset and duration. Time to onset (days) and duration of first occurrence (days) will be summarized. In addition to descriptive statistics (mean, median, min, max), time to onset will be summarized in categories of 0-2 weeks, >2-4 weeks, >4-8 weeks, >8-12 weeks, >12-18weeks, >18-24 weeks, and >24 weeks, and duration of first occurrence will be summarized in categories of 1-5 days, 6-10days, >10 days.
- Cumulative incidence plot.

Listing will be provided which profiles all categories of AEs of special interest per treatment regimens. Other AEs of special interest may be added later. Depending on the number of events, summary and/or listing may be provided appropriately.

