# 7.4.4. Laboratory Assessments

All protocol-required laboratory assessments must be conducted in accordance with the Time and Events Schedule (Table 19). Only local laboratory assessments are undertaken during the course of the trial and its data must be recorded in the patients CRF.

Clinical chemistry and haematology parameters to be tested are listed in Table 22. Female patients of child-bearing potential will have a serum pregnancy test at Screening; urine pregnancy testing may be done during study treatment, if necessary.

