# Table 22 Clinical Chemistry and Haematology Parameters

#### **Clinical Chemistry Parameters**

- Albumin
- Alkaline Phosphatase
- Alanine Transaminase (ALT) or Serum Glutamic Pyruvic Transaminase (SGPT)
- Aspartate Aminotransferase (AST) or Serum Glutamic Oxaloacetic Transaminase (SGOT)
- Gamma-Glutamyl Transpeptidase (GGT)
- Blood Urea Nitrogen (BUN) or urea
- Calcium
- Creatininec
- Lactate Dehydrogenase (LDH)
- Phosphate
- Potassium
- Sodium
- Total Bilirubinb
- Total Protein

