6. ANALYSIS POPULATIONS

The **Intent-to-Treat Population (ITT)** will consist of all randomized patients whether or not randomized treatment was administered. This population will be based on the treatment to which the patient was randomized and will be the primary population for the analysis of efficacy data. Any patient who receives a treatment randomization number will be considered to have been randomized.

The **Safety Population** will consist of all patients who received at least one dose of randomized treatment and will be based on the actual treatment received. This population will be used for the analysis of clinical safety data.

The **Biomarker Population** will consist of all patients with biopsy performed at screening and at least once during treatment.

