12.7. Clinical Laboratory Evaluations

The assessment of laboratory toxicities will examine the following laboratory tests:

Hematology: Hemoglobin (HGB), White Blood Cell (WBC) count, and Platelet count. Automated WBC differential (expressed as absolute count) for basophils, eosinophils, lymphocytes, monocytes, and total neutrophils.

Clinical Chemistry: Sodium, Potassium, Calcium, Albumin, Total Protein, Blood Urea Nitrogen (BUN), Creatinine, Estimated Creatinine Clearance, Lactate Dehydrogenase (LDH), Gamma-Glutamyl Transpeptidase (GCT), phosphate, and C-Reactive Protein (CRP). BUN, LDH, CRP, Total Protein, and Estimated Creatinine Clearance are not gradable by CTCAE v4.0. For Sodium, Potassium, and Calcium, two bi-directional parameters (hyper and hypo), the tests will be graded by CTCAE v4.0 in both directions.

Liver Function Tests: Aspartateaminotransferase (AST) or Serum Glutamic Oxaloacetic Transaminase (SGOT), Alanine aminotransferase (ALT) or Serum Glutamic Pyruvic Transaminase (SGPT), Alkaline phosphatase, Total bilirubin (total) and Direct bilirubin (only recorded when Total bilirubin $\geq 2 \times$ ULN). All these tests are gradable by CTCAE v4.0.

Coagulation Tests: Prothrombin time (PrT), International Normalized Ratio (INR), and Activated Partial thromboplastin time (aPTT). All tests at screening only.

Laboratory grades will be reported using the Common Terminology Criteria for Adverse Events (CTCAE v4.0).

Summary of lab values and change from baseline by scheduled visits using mean, median, standard deviation, minimum and maximum will be provided.

Summaries of lab data by maximum toxicity grade will be provided.

Coagulation tests are only collected at baseline. Therefore this/these test(s) will not appear in any summaries of changes from baseline.

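### Hyperglycaemia is an adverse event of special interest for dabrafenib and for the combination, but no scheduled glucose test exists to find it

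*SAP*

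**What the plan says.** **Event.** SAP 12.3 gives a separate AESI list for each regimen. The dabrafenib monotherapy list includes "Hyperglycemia events" and the combination list includes "Hyperglycaemia events". The trametinib monotherapy list has no such entry.

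**Displays.** The same section plans one table per regimen by AESI category, preferred term and maximum grade (Tables 3.1600 and 3.1800 for the two regimens concerned). For selected AESIs seen in more than 5 subjects on a regimen, it adds event characteristics, time to onset in bands, duration of first occurrence in bands, and a cumulative-incidence plot. SAP 18.1.3 assigns these displays to the Safety Population, which "will consist of all patients who received at least one dose of randomized treatment and will be based on the actual treatment received" (SAP 6).

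**Laboratory measurement.** Protocol 7.4.4 states: "Clinical chemistry and haematology parameters to be tested are listed in Table 22". Table 22 has no glucose entry. The SAP 12.7 chemistry list opens "Clinical Chemistry: Sodium, Potassium, Calcium, Albumin, Total Protein, Blood Urea Nitrogen (BUN), Creatinine, Estimated Creatinine Clearance, Lactate Dehydrogenase (LDH" and goes on to GGT, phosphate and C-reactive protein, again without glucose. The Time and Events Table schedules chemistry and haematology at Screening, every 4 weeks and End of Study, analysed by the local laboratory, and shows no separate glucose row.

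**The concern.** The sponsor has singled this event out for detailed safety reporting, yet the plan contains no scheduled measurement that would reveal it. A patient with raised glucose and no symptoms is counted only if the site orders a glucose test for its own reasons. Because SAP 12.7 omits glucose as well, no graded laboratory summary would expose cases that were never reported as adverse events.

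Two things are at stake. A low or zero count could be taken as evidence that the risk is absent, when it may only mean that nobody looked. And the onset and duration summaries, if produced, would describe the timing of ad hoc tests as much as the course of the event. Asymptomatic cases would also go unnoticed in patients who are still on treatment.

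**Working it through.** The point is structural, and the plan states no hyperglycaemia rate, so there is no figure to reproduce. The check sets the sections side by side.

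1. **Named as an AESI?** Yes, for dabrafenib monotherapy and for the combination (SAP 12.3).
2. **In the protocol panel?** No. The 14 chemistry analytes of Table 22 are albumin, alkaline phosphatase, ALT, AST, GGT, BUN or urea, calcium, creatinine, LDH, phosphate, potassium, sodium, total bilirubin and total protein. The haematology list has no glucose either.
3. **In the SAP laboratory analysis?** No. It is absent from the haematology, chemistry, liver and coagulation lists of SAP 12.7.
4. **Scheduled anywhere else?** No. The Time and Events Table has no glucose row, and the laboratory work-up for pyrexia (Protocol 5.8.5.1) does not name it. In the protocol the word occurs only within the enzyme name G6PD and the name of the PET tracer.
5. **Remaining routes into the tables.** Protocol 7.4.2.5 collects adverse events from first dose to 30 days after discontinuation. Protocol 7.4.2.3 turns a laboratory abnormality into an adverse event if the investigator finds it clinically significant, or if it led to an intervention. Both routes need a symptom or a test that was actually done.
6. **Comparison with other AESIs.** Hepatic events have ALT, AST and bilirubin; renal events have creatinine; neutropenia has the white-cell differential; cardiac events have scheduled ECHO. For post-baseline eye examinations, which are done only when clinically indicated, SAP 12.8 restricts reporting to listings. Hyperglycaemia has neither a scheduled measure nor that restriction.

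**Illustration of the consequence.** Let p be the true proportion of patients with the event and q the share of those cases that is detected and reported. Both are assumptions; the documents give neither. The reported proportion is then p × q. The regimen sizes are inferred from the design: 54 / 3 = 18 patients on dabrafenib monotherapy, and up to 54 on the combination. The probabilities below treat patients as independent.

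| Regimen and assumed p | Quantity | q = 1 | q = 0.5 | q = 0.25 |
|---|---|---|---|---|
| Dabrafenib, N = 18, p = 20% | Expected reported cases, 18 × p × q | 3.6 | 1.8 | 0.9 |
| Dabrafenib, N = 18, p = 20% | Chance of no case, (1 − pq)^18 | 1.8% | 15.0% | 39.7% |
| Dabrafenib, N = 18, p = 30% | Chance of more than 5 cases | 46.6% | 4.2% | 0.1% |
| Combination, N = 54, p = 10% | Chance of more than 5 cases | 45.7% | 5.2% | 0.2% |

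The table shows direction and mechanism only. Incomplete detection makes a zero count more likely, and it can keep the event below the threshold at which the onset, duration and cumulative-incidence displays are produced.

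**The case against.** The strongest case on the other side has four parts.

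**An AESI category is not a promise of measurement.** SAP 12.3 identifies AESIs by searching MedDRA terms among reported events, with the list settled by the safety review team at reporting. Pancreatitis and pulmonary embolism have no scheduled test either, and percentages over exposed patients are the usual convention for adverse events. This stands as a description of the method. It does not remove the gap, because hyperglycaemia is a laboratory finding that one more analyte on an existing sample would detect.

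**Capture is not nil.** A reader might infer that the trial has no ascertainment of this event at all. The documents do not support that: adverse events are collected throughout, significant local results must be recorded, and Protocol Section 7 allows additional safety tests to be requested. What is missing is scheduled glucose testing.

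**The bias cannot be sized.** It is tempting to say that the rate is understated in proportion to the share of patients left untested. That holds only if testing is unrelated to glycaemia. Sites would plausibly test patients with symptoms or known diabetes, so the share of cases found could exceed the share of patients tested. The documents give neither share.

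**Some feared misreadings have no display behind them.** SAP 8.2 provides no safety summaries by centre, SAP 7 makes no treatment comparison, and no person-time rate is planned. Claims about distorted contrasts between centres or regimens therefore fail. Nor does the SAP spell out the AESI denominator: the Safety Population is assigned, but the number of patients on each regimen is not defined.

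This is also a descriptive biomarker study of about 54 patients whose named safety interest is cutaneous. That limits the weight of the point but does not answer it.

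**Conclusion.** The mismatch is real. The plan reports hyperglycaemia by grade, and potentially by onset, duration and cumulative incidence, while no scheduled test supports the count. Its frequency is likely understated, by an amount that cannot be derived from the documents; the figures in the table rest entirely on assumed values of p and q. The conclusion assumes only that some cases are asymptomatic and that not every site tests glucose routinely.

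No primary or efficacy result is affected. The event is not invisible, and the percentage need not be withdrawn from the tables: a reader told how the event was ascertained can interpret it. The point merits correction because the repair is cheap and a sponsor-named risk could otherwise be misread as absent.

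**What to change.** **Preferred.** Add glucose to Protocol Table 22 and to the chemistry list in SAP 12.7, measured on the local sample already drawn at Screening, every 4 weeks and End of Study. Summarise it by CTCAE v4.0 grade with the other gradable tests, and state whether the sample is to be fasting. The Screening value would help to separate pre-existing from emergent hyperglycaemia. That matters because Protocol 4.1.3 names only uncontrolled diabetes, as a risk factor for retinal disease.

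**Cost.** A minor amendment, one analyte on an existing sample and one eCRF line. Patients already enrolled may have no baseline or early values. The documents do not give enrolment status, but the SAP cites a guidance effective in October 2014, a year after Amendment 01 of October 2013, so this limitation may be material.

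**If data collection is too far advanced.** Footnote Tables 3.1600 and 3.1800, and any hyperglycaemia entry in the related onset, duration or cumulative-incidence displays, to say that the event is investigator-reported without scheduled glucose testing and that a low or zero rate does not show absence of the risk. If local results are retrievable, give the number of patients with any post-baseline glucose value. This costs a few lines of text.

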## 1.1.3. BRAF and MEK Inhibitors as Combination Therapy

A 4-part Phase I/II study (BRF113220) investigating the dabrafenib/trametinib combination is being conducted in patients with V600 BRAF mutation-positive solid tumours.

In Part B, patients were treated on 4 escalating dose levels of dabrafenib/trametinib (mg BID/mg once daily): 75/1, 150/1, 150/1.5, 150/2. Demographic and efficacy data for the melanoma patients and safety data for all 125 Part B patients were reported (Flaherty, 2012a).

Among 77 treatment-naïve patients with BRAF V600 mutation-positive melanoma and measurable disease according to Response Evaluation Criteria in Solid Tumours version 1.1(RECIST 1.1), median age was 52 years, 61% male, 57% ECOG performance status of 0, 91% V600E, 65% M1c stage, 26% prior brain metastases, and 52% LDH > ULN. Confirmed ORR was 56% (95% CI: 44.1%-67.2%) with 4 complete response (CR), 39 partial response (PR), 29 stable disease (SD) and 3 PD. Confirmed response rates for each dose level tested in Part B were 67% (n=6), 64% (n=22), 44% (n=25), and 63% (n=24), respectively. Median PFS was 7.4 months overall (95% CI: 5.5-9.2), and 10.8 months (95% CI: 5.3, not reached) in the cohort treated with 150/2. Median duration of response for the entire cohort was 11.3 months (95% CI: 9.2, not reached) with a median duration on treatment of 10.7 months (including 38% of patients ongoing at the time of the analysis). The most common adverse events (AE) were pyrexia (52%), rash (45%), chills (38%), fatigue (37%), and nausea (34%). There were two grade 5 adverse events (AEs), pneumonia and hyponatraemia. The most common Grade 3/4 AEs were pyrexia (n=6, 5%), fatigue (n=6, 5%) and dehydration (n=6, 5%). Skin toxicity > Grade 2 occurred in 17 (14%) patients. Cutaneous squamous cell carcinoma occurred in 3 (2%) patients and actinic keratoses in 2 (2%). The most common treatment related AEs ( $\geq 20\%$ , all grades) among patients in Part B receiving 150 mg BID dabrafenib and 2 mg once daily

trametinib (n=79) were pyrexia (58%), skin toxicities including rash (42%), chills (37%), fatigue (38%) and nausea (34%).

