3. STUDY DESIGN

This is a three-arm, open label, randomized, Phase II study comparing the upfront combination of dabrafenib (GSK2118436) with trametinib (GSK1120212) versus the combination after eight weeks of monotherapy treatment with dabrafenib or trametinib.

Approximately 54 eligible patients with histological confirmed cutaneous melanoma that is either metastatic or unresectable (stage IIIc or IV) and BRAF V600E/K mutation positive as determined by a local laboratory will be randomized, 1:1:1 to one of the three treatment arms.

- Arm A: dabrafenib 150mg BID continuously during eight weeks followed by the combination of trametinib 2mg once daily with dabrafenib 150mg BID until disease progression, death or unacceptable toxicity.
- Arm B: trametinib 2mg/day continuously during eight weeks followed by the combination of trametinib 2mg once daily with dabrafenib 150mg BID until disease progression, death or unacceptable toxicity.
- Arm C: trametinib 2mg/day plus dabrafenib 150mg BID continuously until disease progression, death or unacceptable toxicity.

Monitoring will be performed throughout the study according to the Time and Events Table in the protocol.

Biomarker analysis will be performed on blood, tumor and skin samples according to the Time and Events Table in the protocol.

Clinical responses will be evaluated using RECIST 1.1 criteria every 8 weeks. The response evaluation may be performed earlier if clinically indicated (for example, if

patient has symptomatic deterioration suggesting rapid disease progression or to confirm clinical response at 4 weeks after achieving response).

Patients who show either radiographic or clinical progression of disease according to the investigator during the monotherapy treatment period in arm A or B will be able to go on to the combination treatment before completion of the 8 weeks monotherapy treatment. Patients will be treated with the combination treatment until disease progression; unacceptable toxicity or withdrawals from study whichever comes first.

The study will be considered completed when all patients ended study treatment either through progression, death or withdrawal from study for any reason.

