8. GENERAL CONSIDERATIONS FOR DATA ANALYSES

8.1. Reporting Conventions

Data will be listed and summarized according to GlaxoSmithKline (GSK) current reporting standards where applicable. Integrated Data Standards Library (IDSL) standards will be followed, as appropriate. Reporting and analyses will be performed

using SAS, Version 9.2 or higher. These SAS programs will be imported into HARP and the final output will be produced by running drivers in HARP. Final delivery of all statistical displays will be generated using Clinical Data Interchange Standard Consortium (CDISC) standards. Other software may be used as needed.

Deviations from the analysis in the RAP will be identified in the Clinical Study Report (CSR).

Unless otherwise stated, all listings will be sorted by centre, subject number, and visit. Unless otherwise stated, continuous variables will be summarized with the statistics mean, median, standard deviation, minimum, and maximum. Categorical variables will be summarized with frequency counts and percentages.

Unscheduled visits will be included in the listing using actual time and in calculation of maximum or minimum value over time. However, unscheduled visits will not be included in summaries by planned time.

For summary by planned time, not all plan times are needed to be included in the summary table.

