9.2.1. Reference dates

There are three reference dates:

- Because age is an eligibility requirement, the reference date for age is the date of screening.
- The safety reference date is the treatment start date, and will be used to calculate study day for safety measures.
- The efficacy reference date is the date of randomization and will be used to calculate study day for efficacy measures and baseline characteristics (such as time since initial diagnosis), as well as efficacy durations.

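### Per-regimen AESI percentages set about 8 weeks of monotherapy beside open-ended combination with no exposure adjustment, and combination onset has no time zero of its own

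*SAP*

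**What the plan says.** SAP section 12.3 presents AESIs by category, preferred term and maximum grade "in one table per treatment regimen (dabrafenib monotherapy, trametinib monotherapy, and dabrafenib plus trametinib combotherapy". These are Tables 3.1600, 3.1700 and 3.1800. Section 12.3 names no statistic for them, so the rule in SAP section 8.1 applies: "Categorical variables will be summarized with frequency counts and percentages".

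The windows behind the tables differ. SAP section 3 gives Arm A "dabrafenib 150mg BID continuously during eight weeks followed by the combination", and Arm B the same length of trametinib. Patients who progress early "will be able to go on to the combination treatment before completion of the 8 weeks monotherapy treatment", which shortens their monotherapy further. For the combination, the same section says: "Patients will be treated with the combination treatment until disease progression; unacceptable toxicity or withdrawals from study whichever comes first". The combination AESI list is introduced as "For subjects receiving dabrafenib and trametinib in either the combination arm of after 8 weeks of monotherapy", so it pools Arm C from day 1 with Arms A and B after the switch.

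SAP section 12.1 summarises exposure to each drug separately, not by regimen. On timing, SAP section 9.2.1 states: "The safety reference date is the treatment start date, and will be used to calculate study day for safety measures". SAP section 9.3.1 defines one on-therapy period from first to last dose and does not split it at the switch. Section 12.3 also plans onset summaries and a cumulative incidence plot per regimen (Figures 13.0100, 13.0200 and 13.0300), but only for selected AESIs seen in more than 5 subjects on that regimen.

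**The concern.** A crude percentage depends on how long patients are observed. Here the observation window is a feature of the regimen: capped for monotherapy, uncapped for combination. The SAP gives no person-time rate, common window, regimen denominator or rule for assigning an event at the switch. If the underlying rates were the same, the combination table would still tend to show the higher percentage.

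This matters because a secondary objective is to characterise safety in monotherapy and/or in combination, naming squamous cell carcinoma and rash. All eight AESI categories listed for dabrafenib monotherapy recur on the combination list, so readers will put the tables side by side.

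The second, separate issue is time zero. Section 12.3 does not define it for onset or for the cumulative incidence plots. If first study dose is used by default, the combination displays mix two clocks.

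**Working it through.** The documents state no AESI rate, regimen exposure or ratio, so there is no plan figure to reproduce. The check asks what the crude percentages would show if both regimens had the same constant event rate.

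**Inputs from the documents**
- Monotherapy window: 8 weeks (SAP section 3).
- Final analysis: after the last patient's Week 16 efficacy assessment (SAP section 4.2). This is the minimum follow-up: 8 combination weeks in Arms A and B, 16 in Arm C.
- 54 patients randomised 1:1:1, so 18 per arm (SAP section 5.1).
- "median duration on treatment of 10.7 months" in the earlier phase I/II combination study (Protocol section 1.1.3): 10.7 × 30.4375 / 7 = 46.5 weeks, or 5.8 times 8 weeks.

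**Assumptions not in the documents:** 8-week risks of 2% to 40%, accrual of 0 to 24 months, constant hazard, and exponential treatment duration in the simulation.

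**Formula.** With 8-week risk p, the weekly rate is λ = −ln(1 − p)/8, and the crude percentage after T weeks is 1 − exp(−λT). At a Week 16 cut with everyone still on treatment, the pooled combination percentage is [2p + 1 − (1 − p)²]/3. Divided by p, the ratio is (4 − p)/3.

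**Fixed exposure**

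| 8-week risk (monotherapy) | Week 16 cut, pooled A+B+C | Ratio | Ratio, Arm C alone | Combination 46.5 weeks | Ratio |
|---|---|---|---|---|---|
| 2% | 2.7% | 1.33 | 1.98 | 11.1% | 5.5 |
| 10% | 13.0% | 1.30 | 1.90 | 45.8% | 4.6 |
| 28% | 34.7% | 1.24 | 1.72 | 85.2% | 3.0 |
| 40% | 48.0% | 1.20 | 1.60 | 94.9% | 2.4 |

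**Simulated exposure.** Treatment duration is exponential with median 10.7 months, accrual is uniform, and the cut-off is 16 weeks after the last patient enters. Arms A and B count towards the combination only if still on treatment at Week 8. The entries are pooled ratios.

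| Accrual (months) | Mean combination weeks | 2% risk | 10% risk | 28% risk |
|---|---|---|---|---|
| 0 | 10.0 | 1.3 | 1.3 | 1.2 |
| 6 | 19.8 | 2.6 | 2.4 | 2.0 |
| 12 | 27.4 | 3.5 | 3.0 | 2.3 |
| 24 | 38.2 | 4.8 | 3.8 | 2.5 |

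**Early-onset events.** If 80% of events on a regimen occur in its first 8 weeks, the ratio cannot exceed 1/0.8 = 1.25.

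**After correction.** With the same constant rate, events per unit of time at risk give λ on both regimens, and the first-8-weeks incidence gives p on both. The ratio is 1.0 in every constant-rate scenario.

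**Onset.** An Arm A event two weeks after a Week 8 switch falls at about Week 10 on the study clock, in the category for over 8 to 12 weeks. An Arm C event two weeks into the combination falls in the 0 to 2 weeks category. For both monotherapies and for Arm C, first study dose is also first regimen dose, so only post-switch Arms A and B are affected.

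**Reach of the time-based displays.** More than 5 subjects means 6 of 18 (33%) on a monotherapy, against 6 of 54 (11%) on the combination if all 54 form the denominator (assumed). At a 10% risk, the binomial chance of reaching 6 is 0.6% for a monotherapy and 46% for the combination.

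**The case against.** The strongest reply is that the study is descriptive. SAP section 7 says there is no treatment comparison, the objective is to characterise rather than compare, and the regimens sit in separate tables with different AESI lists. By-arm adverse event tables are also planned, and the onset categories and cumulative incidence plots deal with unequal follow-up. This is correct as far as it goes, and it limits the point to presentation. It does not remove it. A descriptive percentage still needs a stated denominator and window. The by-arm tables merge both phases in Arms A and B. The plots are unlikely to appear for a monotherapy unless incidence is around one third. A reader could roughly estimate phase lengths by subtracting one drug's duration from the other's within Arm A or B, but the combination AESI table pools three arms.

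Three stronger readings are tempting and are not supported:
- A reader might infer that a 4- to 5-fold distortion is to be expected. That needs long follow-up, low-risk events and a constant rate. The 10.7 months is a median from another study pooling four dose levels, and this trial's accrual length is not stated.
- A reader might infer that the onset clock inflates the percentages. It cannot, because moving time zero changes when an event is plotted, not whether it is counted. First study dose is also the default reading of SAP sections 9.2.1 and 9.3.1, not an explicit rule in section 12.3.
- A reader might infer that the squamous cell carcinoma result could reverse. The documents say only that the combination might reduce secondary skin tumours. They give no rates for this trial from which a reversal could be calculated.

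**Conclusion.** The point holds as a conditional one. The planned AESI tables report crude percentages over windows that differ by regimen, and the distortion runs towards higher figures on the combination. Its size is about 1.2 to 1.3 times at the Week 16 minimum, about 2 to 3.5 times with 6 to 12 months of accrual, and up to about 5.5 times with 46.5 weeks of combination exposure. For events concentrated in the first 8 weeks it is near 1. These figures rest on assumed event rates, an assumed accrual period and, except in the early-onset case, a constant rate.

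The missing regimen-specific time zero is a second defect. It affects the combination onset table (3.1811) and Figure 13.0300 only. Neither defect touches the primary endpoint or a formal test. This is a cheap improvement to the safety reporting.

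**What to change.** Amend SAP section 12.3 as follows.

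- Assign each AESI to the regimen being taken at onset, and state how events are assigned if one drug is stopped after the combination has begun. The denominator is patients who started that regimen.
- Measure onset and cumulative incidence from the first dose of that regimen.
- Add to Tables 3.1600, 3.1700 and 3.1800 the events per patient-month of regimen exposure (time to first event where first events are counted) and the incidence in the first 8 weeks of the regimen. Both are needed: for early-onset events, a person-time rate alone would be diluted by the longer combination exposure.
- Show Arm C separately from post-switch Arms A and B, whose patients have already been through a monotherapy phase.

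The cost is a few extra columns and some programming. Treatment start and stop dates are already collected (Protocol section 5.7), so no new data or visits are needed.
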